4.1 Overall Study Design

This double-blinded, randomized, controlled study will be conducted at the University of Virginia. The study will use the experimental rhinovirus human challenge model.

4.1.1 Number of subjects

Approximately 900 volunteers will be recruited for participation in these studies. Volunteers seronegative to rhinovirus type 39 will be randomly treated for 42 days with either:

- probiotic (n=130)
- placebo (n=130)

4.1.2 Study center

The study will take place at the University of Virginia, Charlottesville.

4.2 Assessments and Procedures

4.2.1 Study Conduct

The study will be done in five cohorts of 60-70 subjects each for logistical reasons. The first cohort will be conducted in the Spring of 2016. Subsequent cohorts will be done in Fall 2016, Spring 2017, Fall 2017 and Spring 2018. The assays and data collection for analysis of the primary and secondary efficacy endpoints will be substantially complete by December, 2018.

4.2.2 Study periods

Screening:

- Consent and enrollment (approximately 375 subjects)
- Medical history questionnaire and demographics
- Vital signs and brief physical exam
- Physical activity question
- Review of inclusion/exclusion criteria
- Blood draw for screening neutralization antibody titer (if no antibody screening test has been done in the last 12 weeks)

Day -42 ± 4:

- All subjects begin dietary “run-in” period

Day -28 ± 4: Seronegative subjects only

- Review of inclusion/exclusion criteria
- Pre-probiotic baseline nasal lavage for IL-8 and other cytokines
- Pre-probiotic baseline nasal swab for microbiomics
- Pre-probiotic baseline throat swab for microbiomics
- Blood draw for pre-probiotic transcriptomics studies
- Assessment of concomitant medications
- Randomized to active or placebo probiotic
- Urine pregnancy screen for females

Day -21 ± 2

- All subjects return to study site for new supply of probiotic and compliance review
- AE assessment
- Assessment of concomitant medications

Day -14 ± 2:

- All subjects return to study site for new supply of probiotic and compliance review
- Nasal lavage for multiplex cytokine assays
- AE assessment
- Assessment of concomitant medications

Day -7 ± 2:

- All subjects return to study site for new supply of probiotic and compliance review
- AE assessment
- Assessment of concomitant medications

Day 0:

- Review of inclusion/exclusion criteria
- Assessment of blinding
- AE assessment
- Assessment of concomitant medications
- Urine pregnancy screen for females
- Stool specimen for probiotic compliance and microbiomics
- Nasal swab for microbiomics
- Throat swab for microbiomics
- Throat swab for culture
- Nasal lavage for unanticipated viruses
- Nasal lavage for pre-RV challenge baseline IL-8
- Blood draw for measurement of neutralizing antibody
- Blood draw for pre-RV challenge transcriptomics
- Nasal lavage for multiplex cytokine assays
- Symptom assessment
- Challenge with rhinovirus
- Compliance check/resupply
- Continue probiotic treatment

Day 1-4:

- AE assessment
- Assessment of concomitant medications
- Nasal lavage for quantitative rhinovirus culture
- Nasal lavage for IL-8 measurement
- Nasal lavage for multiplex cytokine assays
- Symptom assessment
- Assessment of the effect of symptoms on physical activity
- Nasal swab for microbiomics (day 3)
- Throat swab for microbiomics (day 3)
- Blood draw for post-RV challenge transcriptomics (Day 2 only)
- Continue probiotic treatment

Day 5:

- AE assessment
- Assessment of concomitant medications
- Nasal lavage for quantitative rhinovirus culture
- Nasal lavage for IL-8 measurement
- Throat swab for culture
- Throat swab for microbiomics
- Symptom assessment
- Assessment of the effect of symptoms on physical activity
- Assessment of common cold illness
- Compliance check/resupply
- Continue probiotic treatment

Day 14

- Return symptom diaries and any remaining study product
- Discontinue probiotic treatment
- Throat swab for microbiomics

Day 21-30:

- AE assessment
- Assessment of concomitant medications
- Blood draw for serum neutralizing antibody

4.2.3 Pre-study safety assessment (Screening)

Volunteers who agree to participate will have a brief medical history and brief physical assessment prior to participation in the study. The purpose of these evaluations will be to detect any underlying condition that would either place the subject at increased risk from the study procedures or that would compromise evaluation of the study endpoints. A medical history questionnaire will be completed by all study subjects. The completed questionnaire will be reviewed with study personnel and all positive responses clarified. A brief physical examination consisting of pulse, respiratory rate, body temperature, blood pressure, and visual examination of the nose will be performed on all subjects and all female subjects will have a urine pregnancy screen. The urine pregnancy screen will be repeated on Day 0 prior to virus challenge. Subjects will be asked whether they exercise at least 30 minutes 3 times each week over the last 3 months. All subjects must meet the inclusion criteria and must not meet any of the exclusion criteria for participation in the study.

4.2.4 Nasal lavage (Study Day -28, -14, and 0-5)

Nasal lavage will be collected for virology and for determination of IL-8 and other cytokine concentrations. These specimens are collected by instillation of 5 mL of sterile 0.9% saline into each nostril. This wash is then immediately expelled into a waxed paper cup and kept chilled until processed.

4.2.5 Blood for transcriptomics (Study Days -28, 0, and 2)

Blood specimens will be collected into PaxgeneRNA extractor tubes for subsequent analysis of gene expression by microarray. These specimens will be handled according to the manufacturer's instructions and stored at -70C until they are analyzed.

4.2.6 Nasal and throat swab sample collection (Study Day -28, and 0, 2, 3, 5, 14)

Nasal swabs will be collected and stored at -70C. Nasal swabs will be collected by inserting a moistened nylon flocked swab (FloQswabs, Copan Diagnostics Inc, Murrieta, CA) into each naris until resistance is met. The swab will be gently rotated and then withdrawn. Pharyngeal swabs will be done using the same swab material to swab the posterior pharyngeal wall. The nasal swabs and throat swabs will be collected before the daily dose of the study product. All throat swabs will be collected by a study nurse experienced in the procedure.

4.2.7 Assessment of Compliance (Study Days -21,-14,-7, and 0-14)

At each study visit during the pre-challenge dosing period, volunteers will be asked to return unused study product to the study site. Compliance will be assessed by counting missed doses of study product. For purposes of the per protocol analyses, the subject will be assessed as compliant with the protocol if at least 80% of the planned doses were taken. In addition, DuPont Nutrition and Health will measure the amount of *Bifidobacterium animalis* subsp. *lactis* from the fecal samples using qPCR.

4.2.8 Stool sample collection (Study Day 0)

Fecal samples will be collected into an air tight container and frozen. The subjects will be given stool sample containers, outer packaging for hygienic storage and delivery and written instructions including sampling and clinic visit dates at a visit prior to sample collection. A prior notice as a reminder will be sent to all subjects before the sampling and clinic visit day. All samples will be marked with study subject code and date.

The stool samples should be:

- defecated on the same day
- kept in a refrigerator or on ice before transport to the clinic
- immediately frozen to -70°C at the clinic
- kept frozen at all times until analysis

4.2.9 Assessment of blinding (Study Day 0)

Volunteers will be asked whether they believe they are receiving active or placebo product. On study day 0, before challenge with the study virus, each volunteer will indicate their response to the following question:

Which treatment do you think you are taking: active control don't know

4.2.10 Challenge with rhinovirus (Study Day 0)

The challenge virus to be used in this study is rhinovirus, type 39, a serotype that attaches via the ICAM-1 receptor. Inoculation will be with a challenge pool of virus that has been thoroughly safety tested and approved for use for virus challenge experiments by the FDA (IND #12934). Following a nasal wash, each subject will be given the challenge virus by intranasal drops. The virus is administered in a volume of 0.25 mL/nosril with a calibrated pipette and two inoculations of virus are given several minutes apart. The total virus inoculum will be 20-100 TCID₅₀/volunteer contained in 1 mL of fluid. This procedure is used routinely in the rhinovirus challenge model and results in an infection rate of 85-90% in susceptible volunteers.

4.2.11 Symptom scoring (Study Days 0-14)

Symptom scores on study days 0-5 will be collected in an interactive interview with the study staff. Symptoms will be assessed using the modified Jackson criteria. On study days 6-14, volunteers will be asked to complete a symptom diary that will consist of the same symptoms assessed by the Jackson criteria. Volunteers will also be asked whether their symptoms affected their physical activity.

5 Study Product

5.1 Study Product and Comparator

5.1.1 Investigational product

The study product will be a 2×10^9 cfus of probiotic *Bifidobacterium lactis* BI-04 (DuPont Nutrition and Health) mixed with 1g of sucrose as a carrier. The study product will be manufactured according to GMP and QC guidelines approved by FDA at DuPont production site located at Madison Wisconsin, USA.

5.1.2 Placebo

Placebo will be 1g of sucrose that has identical appearance, smell, and taste with the study product.

5.2 Supply, Packaging, Labeling, Handling and Storage

Investigational product and placebo product will be released by DuPont Nutrition and Health Qualified Person (QP) and then sent to [name], [name], University of Virginia School of Medicine, [name]. Study products will be packaged and labeled by number for each individual kit according to the study plan. The individual dose boxes (i.e. kits) will be labeled to include the following information:

- Sponsor study code
- Sponsor's name and address
- Investigational product (name) powder and/or corresponding placebo
- Amount of powder etc. of X g/mg and/or corresponding placebo
- For oral administration only
- Instruction of intake
- Investigator's name and study site
- Kit and Batch number
- Expiry date
- Storage conditions
- For clinical trial use only. Keep out of reach of children.

5.2.1 Study product supply and storage

Study product and placebo will be produced under GMP conditions and will be packaged ready for distribution to the volunteers. The investigational product must be stored in the refrigerator until use (2-8 °C). Sponsor may control the stability of the investigational product by collecting samples from the returned containers after the study end to check the viability of the probiotic bacteria. Study product will be stored in a locked, limited access room at +4 °C under the supervision of the study coordinator.

5.3 Dosage and Administration

5.3.1 Duration of Treatment

All volunteers will sign consent and be screened for study eligibility before randomization to study product. On day -28 of the study, all volunteers will come to the study site, be randomized to study treatment and instructed when to take the first dose of study product. Volunteers will be instructed to take daily one sachet of the study product mixed into a drink that is not hot and does not contain alcohol. The study product will have a minimal of 2×10^9 cfus of BI-04. On days -21, -14 and -7 subjects will come to the study site for re-supply of the probiotic and for evaluation of compliance. On day 0 the volunteers will be challenged with the study virus. After the virus challenge all volunteers will continue the study treatment on through study day 14.

5.3.2 Methods of Assigning Subjects to Treatment

The study product and placebo will be randomized and assigned sequential numbers by the sponsor. Volunteers will be assigned a study subject ID number as they present for the day -28 visit. The randomization number and the number of the study material they are given will correspond to their study number. All study personnel will remain blinded to the product or placebo assignment until all data have been collected and entered into the study database, and the database has been locked.

5.4 Concomitant medications

Volunteers who participate in this study will be asked to refrain from using common cold or allergy treatments for the duration of the study. If in the opinion of the volunteer their symptoms are severe and require treatment, treatment should be limited to acetaminophen and the use of the medication should be reported to the study staff. The use of medications other than common cold treatments will be permitted at the discretion of the investigator. All volunteers will be asked to refrain from the use of NSAIDs or steroids beginning two weeks prior to the virus challenge until the end of the symptom reporting period (study day 14).

Use of antibiotics may have an impact on the investigational product functionality and therefore antibiotic use should be avoided unless explicitly needed as judged by a physician. Volunteers who take antibiotics during the study will be removed from the study.

5.4.1 Concomitant diet

During the dietary intervention period (days -28 to 14) subjects should not use any other probiotic or prebiotic containing products. A list of avoidable and acceptable yoghurt products will be provided to volunteers. Study subjects are advised not to mix the product or placebo with hot or alcohol containing drinks.

5.4.2 Prior medications

Continued use of topical agents, hormonal contraception or hormone replacement therapy, SSRIs, and other anti-depressants will generally be permitted.

5.5 Study Product Accountability

The investigator is responsible for the accounting for all unused and all used investigational product containers. The study eCRFs must have an accurate dispensing/returning log. The third-party dispenser (can be a hospital pharmacy or a study nurse) uses this information to

maintain an accurate and complete dispensing and inventory record. The designated copies of the completed dispensing and inventory record will be returned to the sponsor. Supplies are shipped to the investigative site as needed. Study product accounting will be reviewed by the site monitor during routine monitoring visits. At the completion or termination of the study, a final study product accountability review and reconciliation must be completed, and any discrepancies must be investigated and their resolution documented. All full, partially full, and empty containers of study products must be returned to the sponsor with the appropriate form. The sponsor then destroys all and documents the destruction.

6 Response Variables and Study Endpoints

6.1 Assessment of Efficacy

6.2 Primary endpoint

6.2.1 *Incidence of rhinovirus-associated illness episodes*

- 6.2.1.1 Rhinovirus infection: Rhinovirus infection will be defined as the isolation of the challenge virus on any of the 5 days (study days 1-5) after virus challenge or a four-fold rise in neutralizing antibody titer to the study virus.
- 6.2.1.2 Symptomatic illness: Symptomatic illness will be defined according to the modified Jackson criteria. Volunteers who have a total symptom score of at least 6 over the 5 days (study days 1-5) after virus challenge and either three days of rhinorrhea or the subjective impression that they have had a common cold illness will be considered to have a symptomatic illness.
- 6.2.1.3 Rhinovirus-associated illness episodes: Volunteers who have both a rhinovirus infection and a symptomatic illness will be defined as having a rhinovirus-associated common cold illness.

6.3 Secondary endpoints

6.3.1 *Duration of illness*

- 6.3.1.1 Duration of illness will be defined as the time between the virus challenge and the end of the illness episode in volunteers who meet the Jackson definition of symptomatic illness. The end of the illness will be defined as the first of two consecutive days with a total symptom score ≤ 1 that occurs after the subject has met symptom criteria for a Jackson cold.

6.3.2 *Incidence of infection*

- 6.3.2.1 Rhinovirus infection will be defined as the isolation of the challenge virus on any of the 5 days (study days 1-5) after virus challenge or a four-fold rise in neutralizing antibody titer to the study virus.

6.3.3 *Viral load during infection*

- 6.3.3.1 Viral load will be assessed by comparing the quantitative virus titer in nasal lavage between the probiotic and placebo groups. For purposes of this calculation subjects with no virus isolate on a study day will be defined as having a quantitative titer of -0.5 (\log_{10}).

6.3.4 *Proportion shedding the virus*

- 6.3.4.1 The proportion of volunteers shedding virus in the placebo group will be compared with the proportion in the probiotic group. Virus shedding will be defined as the

isolation of the challenge virus on any of the 5 days (study days 1-5) after virus challenge

6.4 Exploratory endpoints

6.4.1 Cytokine response of nasal mucosa

6.4.1.1 Interleukin-8 assay: Concentrations of interleukin-8 in nasal lavage are determined with a commercially available ELISA assay (R&D Systems, Minneapolis, MN). The lower limit of detection for the assay is 31.25 pg/mL. The precision of the assay for measurement of IL-8 in nasal wash has been determined with pools of nasal wash spiked with known concentrations of IL-8. Intra-assay variability was found to range from 3.8-5.7% and inter-assay variability was found to range from 2.7-11% for nasal wash containing high and low concentrations of IL-8, respectively. The recovery of IL-8 in nasal wash ranged from 88-136% of predicted. Specimens that have IL-8 concentrations greater than the operating range of the assay will be diluted 1:10 and 1:100 and re-assayed.

6.4.2 *Multiplex assays: A panel of cytokines and chemokines (TGF- β 1, GCSF, GMCSF, IFN- γ , IL-1 α , IL-12p70, IL-15, CCL20, IL-1 β , IL-6, IL-10, CXCL10, CCL2, CCL3, CCL5, TNF- α) may be measured in nasal lavage fluid using a commercially available multiplex assay (Aushon BioSystems, Inc., Billerica, MA). A determination of which assays will be included will be made as a post-hoc exploratory analysis. Blood transcriptomics*

6.4.2.1 Collection of specimens: The effect of probiotics on gene expression before and after rhinovirus challenge will be determined by comparing expression in the probiotic and placebo groups on study days -28, 0 and 2. Expression analysis will be done on peripheral blood specimens by microarrays targeted at inflammatory and antiviral genes. Blood samples will be collected in PAXgene RNA tubes (PreAnalytix) and stored at -80°C until shipping. Samples will be shipped on dry ice to DuPont Haskell Global Centers for Health and Environmental Science and immediately stored at -80°C until further processing. RNA will be isolated from blood stored in PAXgene tubes using a PAXgene Blood RNA isolation kit (Qiagen) and potential DNA contamination will be removed with on-column DNase treatment. RNA concentration and quality will be verified on a Nanodrop® spectrophotometer (NanoDrop) or with a Quant-iT™ RiboGreen® RNA Assay Kit (Thermo Fisher). RNA integrity will be determined with an Agilent Bioanalyzer 2100 (Agilent). All RNA samples processed for RNA-sequencing should have a 260/280 absorption ratio greater than 2 and a RNA integrity number (RIN) greater than 9.8.

6.4.2.2 RNA-seq: Targeted RNA-seq library preparation will be conducted with Tempo-Seq (BioSpyder) detector oligos designed against a ~1500 human gene panel focused on innate immunity and antiviral defense genes. Library preparation will be conducted in 96 sample batches. Up to 2 library preparations (n=192 samples) will be pooled, purified, quantitated and stored frozen prior to RNA-sequencing. The pooled libraries will be sent to the Pioneer core genomics facility in Johnston, Iowa for RNA-seq using an Illumina NextSeq, or HiSeq platform. The target read-depth per sample will be 1.5 million reads to ensure 500-1000 reads per gene. The reads will be quality filtered, trimmed and demultiplexed by the technical staff in Johnston. The resulting FASTQ files will be transferred via external hard drive, or through the DuPont network for further processing. Backup FASTQ files will be archived at the Johnston facility. The FASTQ files will be aligned to an annotated reference to determine the number of reads per gene. The reads will be quantitated by

normalizing with control genes in the samples set. Other quantitation methods may be considered as well. Data will be stored in this format until the samples can be decoded for further analysis. Once decoded, metadata will be added to the data files to add additional annotation to the sample identifiers and group samples according to experimental conditions. Differential expression analysis will be conducted to determine transcripts that are up or down regulated between the experimental conditions.

6.4.3 *Rhinovirus type-specific antibody response*

6.4.3.1 The effect of probiotic on host antibody responses to the challenge virus will be determined by comparing the convalescent neutralizing antibody titer in the probiotic and placebo groups.

6.4.4 *Fecal, throat and nasal microbiota*

6.4.4.1 Bacterial DNA will be isolated from the swabs and feces by using MagMAX™ Total Nucleic Acid Isolation Kit (Applied Biosystems, Bridgewater, NJ). Human DNA may be quantified for analysing the ratio of human and bacterial DNA by using housekeeping genes that do not allow subject identification. The composition of microbiota will be analyzed by next-generation sequencing (or equivalent) technology for identification of microbial species in the samples. The data will be analyzed to determine effects of probiotic on both abundance and diversity of bacterial species. . In addition, single strain targeting PCR-based molecular methods (i.e. qPCR, digital PCR or equivalent) will be applied to detect the supplemented probiotic strain, BI-04.

6.4.4.2 Throat swabs will be collected on study days 0, 5, and 14 for detection of pharyngeal pathogens by culture and qPCR. A single swab will be sent to the microbiology laboratory at the University of Virginia for detection of *S. aureus*, pneumococcus, *H. influenza*, meningococcus and group A streptococcus.

6.4.5 *Cold questionnaire comparison*

Performance of the questionnaire used in the West study [5] will be compared to endpoints of this study.

6.5 **Assessment of safety**

6.5.1 *Adverse events*

6.5.1.1 The safety of the study interventions will be assessed by monitoring of adverse events. Volunteers will be asked at each study visit to report any unexpected events whether or not they are apparently study related. Each event will be recorded and an assessment of relatedness to the study interventions will be made by the investigator. Adverse events will be coded according to established standards (MedDRA). The analysis will compare both total and related events in the probiotic and the control group.

7 **Adverse Events**

7.1 **Adverse event**

7.1.1 *Definitions*

7.1.1.1 An adverse event (AE) is any untoward, undesired, or unplanned event in the form of signs, symptoms, disease, or laboratory or physiologic observations occurring in a

person given an IP in a clinical study. The event does not need to be causally related to the IP or the clinical study. An AE includes, but is not limited to the following:

- Any clinically significant worsening of a pre-existing condition.
- An AE occurring from overdose of an IP, whether accidental or intentional. Overdose is a dose greater than specified in the protocol.
- An AE occurring from abuse (e.g., use for non-clinical reasons) of an IP.
- An AE that has been associated with the discontinuation of the use of an IP.

7.1.1.2 Treatment Emergent Adverse Event and Repetition of Adverse Event: An adverse event will be regarded as treatment-emergent if it occurred for the first time after the study product administration or if it was present before, but worsened after the study product administration.

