8.4 STATISTICAL ANALYSIS PLAN

In this chapter the most important analyses are described. Before locking the database and opening the treatment code a statistical analysis plan (SAP) document will be created, where all the analyses including the exploratory analyses will be described in detail. At least the descriptive statistics will be reported for all variables.

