#### Cytokine response of nasal mucosa

Change in Interleukin-8 assay (IL-8) concentrations both from day -28 until virus challenge and from day 0 onwards will be analysed with repeated measures analysis of covariance models (RM-ANCOVA), by including the change from day -28/ day 0 as a response, treatment, baseline covariate (IL-8 at day -28/ day 0), timepoint and the interaction of timepoint and treatment as explanatory variables. The random effect of subject will be included in the model. Model assumptions will be checked with model diagnostics and normality plots. In case normality

assumptions cannot be confirmed, common transformations (log, square root, inverse) will be used. For the analysis 'not detected' values will be replaced with the detection limit / 2. For the change from day -28 analysis the PP dataset will be used, and for the change from day 0 analysis the infected dataset will be applied.

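### Gene-level expression analysis: Day -28 is listed among the comparisons meant to show the probiotic effect, and no gene-level model uses the subject's own Day -28 value as a baseline

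*Protocol*

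**What the plan says.** Protocol 6.4.2.1 (Blood transcriptomics, collection of specimens) states the aim, "The effect of probiotics on gene expression before and after rhinovirus challenge will be determined", and the means: "determined by comparing expression in the probiotic and placebo groups on study days -28, 0 and 2". Section 4.2.2 lists the Day -28 sample as "Blood draw for pre-probiotic transcriptomics studies". Section 5.3.1 has volunteers come in on Day -28 to "be randomized to study treatment and instructed when to take the first dose of study product", so that sample precedes all dosing.

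Protocol 6.4.2.2 describes a targeted RNA-seq assay with "detector oligos designed against a ~1500 human gene panel focused on innate immunity and antiviral defense genes". Its only analysis statement is "Differential expression analysis will be conducted to determine transcripts that are up or down regulated between the experimental conditions". No model, baseline term or subject term is named. Protocol 8.4 leaves detail to the SAP, "where all the analyses including the exploratory analyses will be described in detail".

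In SAP 11.3, the blood transcriptomics part specifies categorical repeated measures models with timepoint, treatment and their interaction. The outcome is cluster membership, and the models apply only if clusters form. Day -28 and Day 0 cluster membership also enters models for duration of illness, shedding, symptoms and immune markers. FDR control is stated for correlations only, and SAP 7 otherwise rules out p-value adjustment. For IL-8, the same section models change with a "baseline covariate (IL-8 at day -28/ day 0") and a random subject effect.

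**The concern.** The Day -28 sample has one natural use, as a pre-treatment baseline for later expression. The protocol instead names that day as one of three arm comparisons through which the product effect is determined, and nothing in either document then uses it as a baseline for any gene.

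Two things are at stake. First, the wording lets a Day -28 arm difference appear among results about the product, although randomisation makes the true difference zero. Second, stable person-to-person differences in expression stay in the error term on Days 0 and 2 when the data to remove part of them are already in hand. The blood transcriptome is the first exploratory objective in protocol 2.2.3. With about 1,500 genes and a strict threshold per gene, precision matters more than it would for a single marker.

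Because no gene-level model is fixed, an unadjusted, change-score or covariate analysis could also be chosen after the data are decoded, and these differ materially in precision.

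**Working it through.** **Figure in the plan.** None is given for transcriptomics. The only sample size, 95 completed subjects per arm, is for the primary endpoint (60% versus 40%, 80% power, two-sided 0.05). It reproduces: (0.24 + 0.24) × (1.960 + 0.842)² / 0.04 = 94.2, so 95 per arm with unpooled variance. With pooled variance the result is 97, and power at 95 per arm is 79.2%. It is used below only as a plausible number per arm.

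**Day -28.** The sample is taken before any product (protocol 4.2.2 and 5.3.1) and allocation is random, so the expected arm difference is zero for every gene.

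**Precision on Day 0 or Day 2.** Let r be the correlation between a gene's Day -28 value and its later value, with equal SDs. The documents give no r, so it is an assumption and a range is shown. Relative to comparing the later value alone:

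- Day -28 as covariate: variance × (1 − r²), standard error × √(1 − r²).
- Simple change from Day -28: variance × 2(1 − r).
- Smallest detectable difference with 95 per arm, 80% power and two-sided 0.05 per gene: (1.960 + 0.842) × √(2(1 − r²)/95) SD.

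| r | Variance, covariate | Standard error cut | Variance, change score | Detectable difference, covariate |
|---|---|---|---|---|
| 0 (same as unadjusted) | 1.00 | 0% | 2.00 | 0.41 SD |
| 0.3 | 0.91 | 5% | 1.40 | 0.39 SD |
| 0.5 | 0.75 | 13% | 1.00 | 0.35 SD |
| 0.7 | 0.51 | 29% | 0.60 | 0.29 SD |

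For example, at r = 0.5, √0.75 = 0.866, a cut of about 13%. A simulation with 95 per arm (4,000 runs for each r) gave covariate variance ratios of 0.92, 0.75 and 0.48 at r = 0.3, 0.5 and 0.7, close to the formula. The change score alone is noisier than no adjustment when r is below 0.5.

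**Power at a strict threshold.** Assume a 0.4 SD effect and alpha 0.001 per gene (neither is in the documents). Without adjustment, 0.4/√(2/95) = 2.757, and power is Φ(2.757 − 3.291) = 30%. At r = 0.5 it is Φ(2.757/0.866 − 3.291) = 46%. At r = 0.7 it is Φ(2.757/0.714 − 3.291) = 72%.

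**Multiplicity, a separate matter.** If no gene is affected, 1,500 × 0.05 = 75 genes are expected at p < 0.05 on any one day. Baseline adjustment does not change this number; only FDR or similar control does.

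**The case against.** The strongest reply is that this criticises silence. The protocol sentence sits under specimen collection and names arms and days, not a model. It does not say that the days are analysed separately or that Day -28 values are ignored. A reader might infer both, and might also infer that three samples from one person are treated as independent groups. The documents establish none of this. The one transcriptomic model that is specified is longitudinal, with a treatment-by-timepoint interaction, and cluster data are passed on per subject. The SAP's list is also expressly a minimum, so a missing gene-level model is incomplete specification rather than a wrong choice.

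It can fairly be added that comparing arms on Day -28 is a legitimate baseline check, that the correlation is unknown with a gain at r = 0.3 of only 5%, and that other models would also be acceptable.

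Most of this stands, and it limits the point. It does not remove it. The SAP was the promised place for the detail, its longitudinal model does not have expression as its outcome, SAP 15 records no deviation for transcriptomics, and the baseline approach is written out for IL-8 in the same section.

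**Conclusion.** The point holds as a low-severity gap with a free improvement. Day -28 cannot show a product effect, and no document specifies a gene-level analysis using the subject's own Day -28 expression. If the Day 0 and Day 2 arm comparisons are carried out as the protocol sentence reads, the standard error is larger than necessary. Adjustment would cut it by about 5%, 13% or 29% at assumed correlations of 0.3, 0.5 or 0.7. The true size cannot be fixed from the documents, and the figures assume equal SDs and a linear relation.

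Three stronger readings are not supported:

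- That the Day -28 comparison is void. It is a valid baseline description and is uninformative only as evidence of effect.
- That chance Day -28 imbalances bias the later results. Under randomisation, unadjusted Day 0 and Day 2 comparisons are unbiased with valid type I error, so the loss is in precision.
- That Day 2 will be compared with Day 0 as if the samples were unpaired. No such contrast is described.

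The endpoint is exploratory, and the primary and secondary conclusions are unaffected.

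**What to change.** In protocol 6.4.2.1 and SAP 11.3 (Blood transcriptomics):

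1. State that Day -28 is the pre-treatment baseline, shown descriptively only, and that the product effect is assessed on Days 0 and 2.
2. Specify one model per gene. The response is normalised log expression on Days 0 and 2. The terms are treatment, day, treatment-by-day, the subject's own Day -28 expression as covariate, and a random subject effect. The Day 0 treatment contrast gives the effect before challenge; treatment-by-day gives the effect on the response to virus.
3. Extend the FDR control already stated for correlations to the roughly 1,500 gene tests, naming the contrasts it covers.

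A constrained longitudinal model with a common Day -28 mean across arms is an equally good choice. It keeps subjects without a usable Day -28 sample, whom the covariate model drops. That could matter because protocol 6.4.2.1 sets RNA quality limits for sequencing.

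The cost is wording and analysis code. No extra samples, visits or subjects are needed.
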